### **10.2.2. PK/PD Relationships**

The relationship between Siplizumab concentration (PK) and PD variables will be presented graphically.

## **11. ANALYSIS OF SECONDARY ENDPOINTS**

### **11.1. Immunophenotyping**

Immunophenotyping via fluorescence-activated cell sorter (FACS) analysis will be conducted frequently during the study to assess the potential for an increased risk of infection, changes in leukocyte subsets and recovery following depletion anticipated with all Siplizumab dosing arms.

These data will be summarized by treatment and subject for the safety population: CD14+, CD3+, CD3+CD4+, CD3+CD8+, CD3-CD19+, CD3-CD56+/CD16+; Lymphocyte: WBC ratio, WBC dual platform.

### **11.2. Lymphocyte Count**

Lymphocyte count will be summarized by treatment arm and visit.

### 11.3. CD2 RO

The magnitude and duration of PD effect of Siplizumab will be measured by peripheral blood CD2-receptor occupancy.

### 11.4. Donor specific antibodies (DSA) results

Blood samples for DSAs (antibodies directed against antigens expressed on donor organs) will be collected and evaluated locally.

### 11.5. Efficacy Analysis

Efficacy analysis will be summarized by treatment arm for the FAS.

- **tBPAR**

Treated biopsy proven acute rejection (tBPAR) is any condition in which the subject receives anti-rejection treatment and is histologically diagnosed as acute rejection according to the 2017 Banff criteria, including borderline rejections. Incidence of tBPAR at 12 months will be summarized.

- **AMR**

Incidence of antibody mediated rejection (AMR) at 12 months will be summarized.

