#### **Interim Analysis:**

A formal interim analysis will occur once 50% of subjects in Cohort 1 and 2 complete their 6month study assessment.

This formal interim analysis will be conducted to assess the safety/tolerability (e.g., AEs, SAEs, clinical laboratory assessments, vital signs, PK data and PK/PD activity (e.g., immunophenotyping and CD2 receptor occupancy). The analysis will also include assessment of biopsy proven acute rejection (BPAR), graft losses deaths, and key safety endpoints. In the event the acute rejection rate exceeds a clinically relevant threshold set forth in the protocol and DMC charter, or the a priori defined stopping rules, enrollment will be suspended to allow for the early termination of any treatment cohort where the benefit/risk of siplizumab is deemed unacceptable.

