# 2 Objectives and Endpoints

Table 2-1 Objectives and Related Endpoints

Objective(s)	Endpoint(s)	
Primary Objective	Endpoints for primary objective	
To assess the safety, tolerability, PK and PD of siplizumab compared to rATG, in de novo renal transplant recipients at 12 months post-transplant.	
 
Adverse events
 
Serious adverse events
 
Clinically significant changes in clinical chemistry, hematology, vital signs, serology
 
siplizumab PK
 
Immunophenotyping
 
CD2 RO
 
eGFR via MDRD
 
	

 
Secondary Objectives
 
To measure changes in peripheral lymphocyte immunophenotype
 
To measure the time-course and duration of siplizumab induced lymphocyte depletion and time to recovery
 
To measure peripheral CD2-receptor occupancy following siplizumab administration over time
 
To assess the incidence of treated biopsy proven acute rejection (tBPAR) at 12 months
 
To assess the incidence of treatment emergent de novo, donor specific antibodies (DSA) at 12 months
 
To assess the incidence of antibody meditated rejection at 12 months
 
To assess repail function via eGER using MDRD equation at
 
	
 
Endpoints for secondary objectives
 
Immunophenotyping via FACS
 
Lymphocyte counts
 
CD2 RO
 
Anti-siplizumab Ab
 
Incidence of BPAR
 
de novo-DSA / anti-HLA antibody measurement
 
incidence of AMR
 
	

 
To assess renal function via eGFR using MDRD equation at Months 3, 6, 12 or EOS
 
		

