#### 8.4.8 **Treated Biopsy Proven Acute Rejection**

Treated biopsy proven acute rejection (tBPAR) is any condition in which the subject receives anti-rejection treatment and is histologically diagnosed as acute rejection according to the 2017 Banff criteria, including borderline rejections, as outlined in Appendix 7.

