### 4. STUDY DESCRIPTION

#### 4.1. Study Objectives and Endpoints

Objectives	Endpoints
Primary	

To assess the safety, tolerability, pharmacokinetics (PK), and pharmacodynamics (PD) of siplizumab compared to rabbit anti-thymocyte globulin (rATG), in de novo renal transplant recipients over 12 months post-transplant.

	

Adverse events

Serious adverse events

Clinically significant changes in clinical chemistry, hematology, vital signs, serology

Siplizumab PK

PK-PD relationship

Secondary	

To measure changes in peripheral lymphocyte immunophenotype

To measure the time-course and duration of Siplizumab induced lymphocyte depletion and time to recovery

To measure peripheral CD2-receptor occupancy following Siplizumab administration over time

To assess the incidence of treated biopsy proven acute rejection (tBPAR) at 12 months

To assess the incidence of treatment emergent de novo, donor specific antibodies (DSA) at 12 months

To assess the incidence of antibody mediated rejection at 12 months

To assess renal function via eGFR using the Modification of Diet in Renal Disease (MDRD) equation at Months 3, 6, 12 or EOS

	

Immunophenotyping via FACS

Lymphocyte counts

CD2-receptor occupancy (RO)

Incidence of tBPAR

de novo DSA/anti-HLA antibody measurement

incidence of AMR

eGFR via MDRD

Exploratory

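### Protocol Table 2-1 pairs a treated-BPAR objective with a BPAR endpoint; the SAP settles on treated BPAR without comment and plans no by-arm summary of all BPAR

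*SAP*

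**What the plan says.** **Protocol, section 2, Table 2-1.** The secondary objective is "To assess the incidence of treated biopsy proven acute rejection (tBPAR) at 12 months"; the synopsis gives the same objective. The endpoint column of the same table says "Incidence of BPAR", with no reference to treatment.

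**Protocol, section 8.4.8.** The only rejection outcome defined is the treated one: "Treated biopsy proven acute rejection (tBPAR) is any condition in which the subject receives anti-rejection treatment", with histological confirmation under the 2017 Banff criteria and borderline rejections counted.

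**SAP, sections 4.1 and 11.5.** The endpoint list reads "Incidence of tBPAR". Section 11.5 takes over the protocol definition ("any condition in which the subject receives anti-rejection treatment and is histologically diagnosed as acute rejection according to the 2017 Banff criteria", borderline included) and states "Incidence of tBPAR at 12 months will be summarized". The only other rejection summary there is "Incidence of antibody mediated rejection (AMR) at 12 months will be summarized", which carries no treatment condition.

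**Interim analysis.** The protocol synopsis says "The analysis will also include assessment of biopsy proven acute rejection (BPAR), graft losses deaths, and key safety endpoints". SAP section 5.1 reports that the interim, run under a separate plan, assessed BPAR.

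**Blinding.** The trial is open-label. Protocol section 4 accepts that knowledge of the arm can affect how subjects are managed, and says that this generally works in favor of the control.

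**The concern.** An objective and its endpoint should name the same quantity, and here they do not. The SAP picks one of the two and does not say that it has done so. A reader who starts from the endpoint column of Table 2-1, or from the interim results, will look for BPAR by arm and find only tBPAR and AMR.

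The two quantities are not interchangeable. tBPAR makes a management decision, taken with the arm known, part of the outcome. A biopsy-proven T-cell-mediated rejection that is left untreated is not in the tBPAR count, while a borderline lesion enters it if the investigator chooses to treat.

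Protocol section 4.2 says that the comparative data are meant to support effect-size estimates for later trials. For that use, it matters which rejection measure is reported and how far it depends on investigator behavior.

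**Working it through.** The documents state no power, event count or calculated sample size for this endpoint, so there is no planned figure to reproduce. The check compares the definitions and then sizes the effect of one subject.

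**Step 1. Which measure is used where**

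| Place | Measure |
|---|---|
| Protocol synopsis and Table 2-1, objective | tBPAR at 12 months |
| Protocol Table 2-1, endpoint | BPAR |
| Protocol 8.4.8, definition | tBPAR, borderline included |
| Protocol synopsis and SAP 5.1, interim analysis | BPAR |
| Protocol 9.1.1 and SAP 4.2.3, stopping rule | BPAR of Grade IIA or higher (TCMR), first 6 months, per cohort |
| SAP 4.1 and 11.5, final analysis | tBPAR at 12 months |

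SAP section 12 (exploratory endpoints) is largely redacted. Its entries in the table of contents show no rejection analysis.

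**Step 2. How the measures differ case by case.** Protocol Appendix 7 puts borderline changes in Category 3, separate from TCMR in Category 4.

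| Biopsy finding | tBPAR | BPAR with borderline | BPAR without borderline |
|---|---|---|---|
| Acute TCMR, treated | yes | yes | yes |
| Acute TCMR, not treated | no | yes | yes |
| Borderline, treated | yes | yes | no |
| Borderline, not treated | no | yes | no |

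BPAR with borderline can therefore only equal or exceed tBPAR. BPAR without borderline can lie on either side of it.

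**Step 3. Can untreated cases be observed?** Yes. Protocol section 8.4.7 requires a biopsy for every suspected rejection whether or not treatment is started. Footnote L of the Schedule of Assessments allows protocol biopsies under local practice.

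**Step 4. Expected events in an arm of 8**, as 8 × rate:
- Protocol section 1.1, US one-year acute rejection, 7% to 8%: 8 × 0.07 = 0.56; 8 × 0.08 = 0.64.
- Protocol section 4, 12-month BPAR with anti-IL2 induction or no induction, 11.7% to 13.3%: 8 × 0.117 = 0.94; 8 × 0.133 = 1.06.

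The second range comes from regimens not used in this trial, so the two together serve as a bracket of about 0.6 to 1.1 events per arm.

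**Step 5. Effect of one reclassified subject:** 1/8 = 12.5 percentage points. With exact (Clopper-Pearson) 95% intervals:

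| Events | Rate | 95% interval |
|---|---|---|
| 0/8 | 0% | 0 to 36.9% |
| 1/8 | 12.5% | 0.3 to 52.7% |
| 2/8 | 25.0% | 3.2 to 65.1% |

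**Step 6. How likely is it that tBPAR omits at least one BPAR?** This needs the untreated share *u*, which the documents do not give. As an assumption, take *u* from 10% to 50%, with independent subjects and one rejection rate *p* in all arms. The probability is 1 − (1 − *pu*)^n.
- Low end, *p* = 0.07 and *u* = 0.10: 1 − 0.993^8 = 5.5% per arm; 1 − 0.993^24 = 15.5% over 24 subjects.
- High end, *p* = 0.133 and *u* = 0.50: 1 − 0.9335^8 = 42.3% per arm; 1 − 0.9335^24 = 80.8% over 24 subjects.

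The range is wide because *u* is unknown. It shows only that an omission is neither negligible nor certain.

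**The case against.** The strongest reply is that the SAP follows the protocol. The secondary objective is tBPAR in both the synopsis and Table 2-1, section 8.4.8 defines only tBPAR, and counting borderline lesions is a protocol choice that the SAP repeats. On this view, all that remains is one unqualified label in one table column. The point about the objective and definition stands: a reader might infer that the SAP replaced the protocol's endpoint with a different one, and the documents do not support that. They show a mismatch inside the protocol that the SAP settled without saying so.

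Three further replies also stand, and limit the point:
- **Untreated cases are not lost.** Protocol section 6.7.1 says acute rejections should be treated, so untreated cases should be uncommon. Biopsy reads and rejection episodes go on the eCRF, and SAP section 8 lists all CRF data by arm and subject. A listing, however, is not an incidence by arm.
- **All-BPAR is not free of open-label influence.** Suspecting rejection and ordering a for-cause biopsy are also unblinded decisions. Protocol section 4 relies on a small number of centers with similar practice to limit such bias.
- **Consistency with the stopping rule is not an argument for either measure.** That rule counts only Grade IIA or higher, over 6 months, so neither 12-month measure would match it.

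Finally, a shift of 12.5 points per subject applies to any binary outcome with 8 subjects. It shows how fragile the rate is, not how often the two measures would differ.

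**Conclusion.** The point holds in a limited form. Table 2-1 pairs a tBPAR objective with a BPAR endpoint, the SAP adopts tBPAR without explanation, and the BPAR endpoint, also used at the interim, has no planned by-arm summary in the SAP text that can be read. The summary that is planned depends on an unblinded decision to treat.

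The practical gap is probably confined mainly to borderline lesions and protocol-biopsy findings. With about 0.6 to 1.1 events expected per arm, one such case would still move an arm by 12.5 points, for example from 1/8 to 2/8. How often that would happen cannot be derived from the documents, because it rests on an untreated share that they do not give.

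The analysis is descriptive (SAP section 8.0), so no error rate, power or sample size is affected. A reader might infer that the tBPAR result will be biased in a known direction. The documents support only the possibility of influence, not its size or its sign in this trial.

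**What to change.** 1. **Protocol Table 2-1:** make the objective and the endpoint name the same measure, or list both. In SAP section 4.1, state how the difference was resolved and why.
2. **SAP section 11.5:** keep tBPAR as defined. Add the 12-month incidence of BPAR regardless of treatment, shown with and without borderline lesions, by arm in the FAS. State that the Clopper-Pearson 95% intervals of SAP section 8 will be presented; that section fixes the method but only for cases where intervals are shown.
3. **Interpretation:** add a sentence saying that the new summary removes dependence on the decision to treat, but not on the unblinded decision to biopsy.

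The cost is one extra descriptive table. It uses the biopsy reads and anti-rejection medication that Protocol sections 8.4.7 and 6.7.1 already send to the eCRF, so no new data collection is needed.

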### 11.6. Renal Function

- **Change from baseline in renal function eGFR**

Renal function will be assessed by eGFR, using an automated calculation factoring serum creatinine, demographics and the MDRD4 formula.

MDRD 4-variable GFR Equation as below:

$$GFR \text{ in } mL/min \text{ per } 1.73 \text{ } m^2 = 175 \times \text{SerumCr}^{-1.154} \times \text{age}^{-0.203} \times 1.212 \text{ (if patient is black)} \\ * 0.742 \text{ (if female)}$$

- **Change from baseline in CKD-EPI**

The CKD-EPI equation are modeled using least squares linear regression to relate log transformed measured GFR to log-transformed filtration markers, age and sex with two slope splines for creatinine, Expressed as a single equation:

$$eGFR = 142 * \min(\text{standardized Scr/K, 1}) \alpha * \max(\text{standardized Scr/K, 1}) \\ - 1.200 * 0.9938 \text{Age} * 1.012 \text{ [if female]}$$

Abbreviations / Units:

*eGFR (estimated glomerular filtration rate) = mL/min/ 1.73 m^2*

*Scr (serum creatinine) = mg/dL*

*K = 0.7 (females) or 0.9 (males)*

*$\alpha = -0.241$  (females) or  $-0.302$  (males)*

*min = indicates the minimum of Scr/K or I*

*max = indicates the maximum of Scr/K or I*

The above parameters will be summarized by visit. This will also be evaluated at Months 3, 6 and 12 (EOS) by comparing the mean eGFR values between groups.

## 12. ANALYSIS OF EXPLORATORY ENDPOINTS

[REDACTED]

(including a category labeled as “missing” when appropriate).

[REDACTED] [REDACTED]

[REDACTED]

[REDACTED]

• occurrence of BK [REDACTED]

• occur [REDACTED]

[REDACTED] [REDACTED]

[REDACTED]

[REDACTED] [REDACTED]

[REDACTED] [REDACTED]

[REDACTED]

[REDACTED]

[REDACTED]

[REDACTED] [REDACTED]

[REDACTED]

A large rectangular area of the document has been completely blacked out, obscuring several lines of text. This redaction is located in the upper portion of the page, above the main table.

## **13. IDENTIFICATION AND SUMMARY OF PROTOCOL DEVIATIONS**

Major protocol deviations from entry criteria and treatment compliance will be summarized as far as they can be extracted from numeric or coded study data.

All protocol deviations, both minor and major, will be presented in a data listing.

## 15. APPENDICES

### 15.1. Appendix A – Imputation Algorithm for Partial and Missing Dates

This section describes missing date imputation methods.

#### **For Adverse Events**

If onset date is completely missing, onset date is set to date of randomization.

If (year is present and month and day are missing) or (year and day are present and month is missing):

- If year = year of randomization, then set month and day to month and day of randomization
- If year < year of randomization, then set month and day to December 31.
- If year > year of randomization, then set month and day to January 1.

If month and year are present and day is missing:

- If year = year of randomization and
  - If month = month of randomization then set day to day of first dose
  - If month < month of first dose then set day to last day of month
  - If month > month of first dose then set day to first day of month
- If year < year of randomization then set day to last day of month
- If year > year of randomization then set day to first day of month

For all other cases, set onset date to date of randomization.

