#### **10.1.2. Adverse Events**

Each AE and SAE term will be recorded as a verbatim term on the case report forms (CRFs). All AEs and SAEs will be coded by primary system organ class (SOC) and mapped to a preferred term using the MedDRA dictionary (version 26.0 or higher). The investigator will assess AE severity and relationship to the study treatment.

All AEs will be listed. However, only treatment emergent adverse events (TEAEs) will be included in the AE summaries. A TEAE is defined as any AE with an onset date on or after the first study treatment dosing date. In addition, any AEs that the investigators deem to be treatment related, regardless of onset date, will also be considered TEAEs and will be included in the AE summaries.

For the purpose of calculating treatment emergence and inclusion in summary tables, incomplete onset dates will be imputed using the method described in Appendix A.

AEs will be summarized by the number and percentage of subjects in each primary SOC and preferred term. Subjects will be counted only once for each primary SOC and each preferred term. Summary tables of AEs by primary SOC, preferred term and severity will be provided. If a subject has more than one AE coded to the same preferred term, the subject will be counted only once for that preferred term by using the event with the highest severity. Similarly, if a subject has more than one AE within a primary SOC category, the subject will be counted only once in that SOC category by using the event with the highest severity. AEs by primary SOC, preferred term and relationship to study drug will be provided as well. If a subject has more than one AE coded to the same preferred term, the subject will be counted only once for that preferred term by using the most related event. Similarly, if a subject has more than one AE within a primary SOC category, the subject will be counted only once in that primary SOC category by using the most related event. In addition, serious adverse events (SAEs) by primary SOC and preferred term will be provided. Deaths and SAEs will be summarized similarly to AEs. All adverse event tables will also include the total number of events, counting multiple events per subject.

In the AE summary, preferred terms within each SOC will appear in alphabetical order.

Frequencies for deaths and hospitalizations will also be summarized by treatment group and overall.

All information obtained on AEs will be displayed by treatment group.

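### SAP Appendix A dates some incomplete AE onsets to randomization rather than first dose, so for subjects randomized the calendar day before dosing these AEs drop out of the treatment-emergent tables unless judged related

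*SAP*

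**What the plan says.** SAP 10.1.2 lists all AEs but restricts the tables: "However, only treatment emergent adverse events (TEAEs) will be included in the AE summaries". The test is against dosing: "A TEAE is defined as any AE with an onset date on or after the first study treatment dosing date". There is one exception: "any AEs that the investigators deem to be treatment related, regardless of onset date, will also be considered TEAEs". For this test, "incomplete onset dates will be imputed using the method described in Appendix A".

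SAP 15.1 (Appendix A, adverse events) then uses the randomization date in three branches:

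- Onset wholly missing: "If onset date is completely missing, onset date is set to date of randomization".
- Month missing, with or without the day: "If year = year of randomization, then set month and day to month and day of randomization".
- Fallback: "For all other cases, set onset date to date of randomization".

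The branch for a missing day works differently: "If month = month of randomization then set day to day of first dose". Its other comparisons within the randomization year use the month of first dose.

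Protocol 3.1 defines Day 0 as the day of transplant and first dose. It asks sites to make every effort to randomize on that day, but permits randomization up to 24 hours before transplant when logistics require it. Protocol Appendix 2 explains the 24-hour window by transplants scheduled in the early morning, which is when randomization is likely to fall on the previous calendar day.

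**The concern.** The date that is imputed and the date it is tested against are different. When they fall on different calendar days, an AE of unknown onset is classed as pre-treatment by construction, although the unknown date is far more likely to lie in the 12 months after dosing than on the single day before it. The usual convention is the reverse: unknown onset counts as emergent unless something shows that it preceded dosing. Appendix A follows that convention in its missing-day branch, and its medication rule treats a wholly missing start as concomitant unless the end date precedes randomization.

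AEs are a primary endpoint (protocol 12.4.1, SAP 4.1), and deaths and SAEs are summarized in the same way. The exception for related AEs is only a partial rescue, because protocol 10.1.1 tells investigators that events due to lack of efficacy will usually be assessed as not suspected.

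A second, connected problem is that treatment emergence has several definitions. Within SAP 10.1.2, the text above counts onset on or after the dosing date, while the sentence introducing the list of tables counts onset after first dose plus pre-existing events that worsened. That sentence comes from protocol 12.5.2, which elsewhere adds events that became suspected or became serious.

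**Working it through.** There is no design figure to reproduce. The check applies the Appendix A rules and the SAP 10.1.2 date test (onset on or after first dose) to each pattern of missing date parts.

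**Worked cases**

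| Randomized / dosed | What is known of onset | Imputed onset | Emergent? |
|---|---|---|---|
| 15 June / 15 June | nothing, or year only | 15 June | yes |
| 14 June / 15 June | nothing | 14 June | no |
| 14 June / 15 June | randomization year only | 14 June | no |
| 14 June / 15 June | 20 September, year missing | 14 June | no |
| 14 June / 15 June | June of that year, day missing | 15 June | yes |
| 30 June / 1 July | July of that year, day missing | 30 June | no |

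In the last row, July is not the randomization month and is neither before nor after the month of first dose. The AE therefore falls to the fallback and is dated pre-dose, although every day in July is on or after dosing.

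**Full enumeration.** Inputs: 365 randomization dates; true onset on Days 0 to 336 (Day 336 is the final visit in protocol Appendix 1), so 337 onset days; 365 × 337 = 123,005 post-dose AEs per pattern. Results for 2022 and 2023 are identical.

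Randomized on Day 0: 0 of 123,005 dated pre-dose in every pattern.

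Randomized on the calendar day before dosing:

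- Onset wholly missing: 123,005/123,005 = 100%.
- Year missing, whatever else is known: 123,005/123,005 = 100%.
- Month missing, year known: an AE is lost if its year is the randomization year. For randomization on day k of the year, min(337, 365 − k) onset days fall in that year. The sum is 28 × 337 + (336 × 337)/2 = 9,436 + 56,616 = 66,052, and 66,052/123,005 = 53.7%. This is 100% of AEs in the randomization year and none of those in the next.
- Only the day missing: the 11 month-end randomization dates from January to November lose every AE in the dosing month, February to December, which is 365 − 31 = 334 days. 334/123,005 = 0.27%.

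A 31 December / 1 January split loses 0 of 337 AEs when the year is known, because an AE in the randomization year really did precede dosing. It loses 337 of 337 when the onset or the year is missing.

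**Overall share.** Share lost = (proportion randomized the day before) × (proportion of AEs in an affected branch) × (proportion judged unrelated). None of the three is in the documents, so these are assumed illustrations, with the trial total also assumed at 240 to 480 AEs:

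- No prior-day randomizations: 0.
- 2 of 24 subjects, 1% of AEs, 30% related: (2/24)(0.01)(0.7) = 0.058%, or 0.14 to 0.28 AEs.
- 12 of 24 subjects, 5% of AEs, 20% related: (12/24)(0.05)(0.8) = 2.0%, or 4.8 to 9.6 AEs.

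If 20% of the lost AEs had worsened and the second SAP definition restored them, the last two shares become 0.047% and 1.6%.

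**The case against.** Three conditions must coincide: prior-day randomization, an affected missing pattern, and an AE judged unrelated. Day 0 randomization is the stated norm throughout the protocol. AE start dates are required (10.1.1), AEs are sought at every visit, SAEs and AEs of special interest are entered within 24 hours (10.1.4), visit data are due within 5 working days (13.4.1), and missing values are queried (13.4.2). AEs lacking a month or year should therefore be rare, and the upper illustration, with half the subjects randomized a day early, is hard to reconcile with those controls. Affected AEs remain in the listings, the analysis is descriptive (SAP 8.0), and no stopping or escalation rule reads these tables. All of this stands. It limits the size of the problem but does not make the rule right.

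Two further points stand as qualifications. First, the zero for Day 0 randomizations holds under the on-or-after definition. If the second definition's wording is read by date, an onset imputed to the dosing date would be excluded there too, so the anchor and the definition need to be settled together. Second, re-anchoring could admit some truly pre-dose AEs, since collection starts after consent and a first invasive procedure, and it gives no date for subjects randomized but never dosed. The stop-date and date-part check in the fix limits the former. The latter are outside the Safety Set, so only listings are concerned.

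**Conclusion.** The point holds. For subjects randomized on the calendar day before dosing, three branches of Appendix A move post-dose AEs to a pre-dose date, and the first definition in SAP 10.1.2 then removes them from the summaries unless they are related. The appendix contradicts its own missing-day branch, and at a month end it dates as pre-dose an AE that can only have occurred on or after dosing.

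The text mismatch is certain; its consequence is not. The conditional losses in the enumeration assume randomization dates uniform over the year and onset uniform over Days 0 to 336. The unconditional share depends on counts that the documents do not give: it is probably small, may be nil, and the 2.0% illustration should carry little weight. In an arm of 8, reported incidence changes, by 1/8 or 12.5 percentage points, only when a lost AE is that subject's sole occurrence of the preferred term. This should be corrected before the final tables are produced, but it does not threaten the trial's conclusions.

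**What to change.** In SAP Appendix A, replace randomization with the first-dose date as the anchor in every AE branch, including the fallback. Impute an unknown onset to the first-dose date unless the AE stop date or the known date parts show an earlier start. State that subjects never dosed appear in listings only, with onset as collected. Under this rule none of the enumerated post-dose AEs is lost in any pattern, and under the on-or-after definition nothing changes for Day 0 randomizations beyond what the stop date or known date parts dictate.

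As a secondary step, adopt a single definition of treatment emergence that reconciles SAP 10.1.2 with protocol 12.5.2: onset on or after first dose; worsening of a pre-existing event after first dose; AEs judged related; and the changed-to-suspected and became-serious criteria where the CRF captures them. Keep on or after, so that an onset imputed to the dosing date still counts.

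The cost is SAP wording plus minor programming: re-anchored branches, a stop-date check and one flag. Protocol 10.1.1 has changes in severity and suspected relationship assessed at each visit, but the documents do not show whether the CRF dates them, which may limit the last two criteria. A few AEs, possibly none, would be added to the tables.
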